8.2 SAMPLE SIZE DETERMINATION

The primary objective of this study is to demonstrate the reduction of depressive symptoms from baseline to 6 months using CALM in PCNST participants. Based on the previous study, we expect a mean difference reduction in depressive symptoms of 1.8 with a standard deviation of the difference of 5.7. To detect this difference, we need 80 participants using a 2-tailed test at 5 significance level and 80% power. To account for estimated attrition of 20%, recruitment of 100 participants to have 80 evaluable participants.

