8.3 STATISTICAL ANALYSIS

8.3.1 Analysis of the Primary Endpoint

To demonstrate the effect of CALM on depressive symptoms using PROMIS-Depression, we will perform a paired t-test from baseline to 6 months using a 2-tailed test at a 5% significance level. One interim analysis is planned when half of the participants have undergone CALM treatment. The study will be stopped early if the absolute nominal statistic for paired differences in depressive symptoms is larger than 2.782 (alpha=.0054) to claim the benefit of CALM. At the end of the study, CALM treatment will be claimed to be a success if the absolute nominal critical point is larger than 1.967 (alpha=.0492). The stopping boundary is based on the O'Brien-Fleming method with 2 interim analyses.

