To evaluate the feasibility of implementing CALM remotely, we will use descriptive statistics to summarize information, including rates of compliance and attrition, and participant satisfaction. This will be evaluated at the interim analysis using the same percentages outlined for the final analysis. The quantity of missing data, the variability of the data over time, and trends over time will be especially important to report to assess the feasibility of CALM. We will report participant satisfaction with the CALM experience using the responses from the WIWI instrument and thematic analysis of participant responses from the interviews. Participant's responses will go through a multi-stage process of categorizing and coding to identify themes associated with the participants experience with the CALM intervention. Results of the analysis will be reported out separately.

We will consider the study to be feasible if the following criteria are met:

- Accrual: Recruitment of 100 participants to have 80 evaluable participants in two years and less than 20% of eligible participants unable to participate due to lack of electronic devices (computer, smartphone, or iPad).
- Compliance: at least 80% of participants completing the outcome measures at all time points

Tolerability and acceptability will be assessed through the WIWI.

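### The two O'Brien-Fleming cut-offs together give a two-sided alpha of 0.0513 at a half-way look, not 5%, and the number of interim analyses is stated two ways

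*Combined protocol and SAP*

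**What the plan says.** All of the decision rule is in section 8.3.1.

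- Test and level: "we will perform a paired t-test from baseline to 6 months using a 2-tailed test at a 5% significance level".
- Timing: "One interim analysis is planned when half of the participants have undergone CALM treatment".
- Interim rule: stop early if the "absolute nominal statistic for paired differences in depressive symptoms is larger than 2.782"; the sentence gives the cut-off with its nominal level as "larger than 2.782 (alpha=.0054) to claim the benefit of CALM".
- Final rule: success if the critical point is "larger than 1.967 (alpha=.0492").
- Source of the boundary: the O'Brien-Fleming "method with 2 interim analyses".

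Section 8.3.2 refers to a single interim when it turns to feasibility: "This will be evaluated at the interim analysis using the same percentages outlined for the final analysis". Section 8.2 gives the sample size: "we need 80 participants using a 2-tailed test at 5 significance level and 80% power", for a mean reduction of 1.8 with an SD of the difference of 5.7.

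**The concern.** A two-look boundary is a matched pair: once the interim value is fixed, the final value follows from the overall alpha and the timing. The values in 8.3.1 have the O'Brien-Fleming shape, but both are lower than that method gives for a two-sided 5% test with a half-way look. These two numbers alone decide whether the study stops early and whether it claims success on its primary endpoint, so they should deliver the level named in the same paragraph.

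Two ambiguities sit beside this. The cut-offs are normal-scale values while the test is a paired t-test, and the text does not say which scale applies. And one interim cannot be reconciled with two: taken literally, two interims plus a final would need three cut-offs, and only two are given.

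**Working it through.** **Inputs.** Two-sided 5%, one look at half, cut-offs 2.782 (.0054) and 1.967 (.0492), all from 8.3.1; 80 evaluable pairs, effect 1.8, SD 5.7, from 8.2. Assumption: half of participants means information fraction f = 0.5, that is 40 of 80 pairs.

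**1. What reproduces.** The nominal levels match the cut-offs: 2 × (1 − Φ(2.782)) = 0.0054 and 2 × (1 − Φ(1.967)) = 0.0492. The ratio 2.782 / 1.967 = 1.414 = √2, which is the O'Brien-Fleming shape for two analyses with the first at half information.

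**2. What does not reproduce.** Under the null, Z1 and Z2 are bivariate normal with correlation √f. The overall level is

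α = 1 − P(|Z1| ≤ 2.782 and |Z2| ≤ 1.967).

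At f = 0.5, numerical integration gives α = 0.05128, against the stated 0.05.

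**3. Values that do hold 5% at f = 0.5.**

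| Condition | Interim | Final |
|---|---|---|
| O'Brien-Fleming (ratio √2) | 2.797 (.0052) | 1.977 (.0480) |
| Keep 2.782, solve the final | 2.782 (.0054) | 1.979 (.0479) |
| Keep 1.967, solve the interim | 3.009 (.0026) | 1.967 (.0492) |
| O'Brien-Fleming-type spending, 2.5% per tail | 2.963 (.0031) | 1.969 (.0490) |
| O'Brien-Fleming-type spending, two-sided 5% once | 2.772 (.0056) | 1.979 (.0478) |

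Neither printed value is impossible alone; it is the pair that fails. Three equally spaced analyses would need 3.471, 2.454 and 2.004, so a second interim does not explain the numbers either.

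**4. Dependence on timing (plan's cut-offs).**

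| Normal scale: f | α | p-value cut-offs: pairs at interim | α |
|---|---|---|---|
| 0.40 | 0.0519 | – | – |
| 0.50 | 0.0513 | 40/80 | 0.0515 |
| 0.625 | 0.0505 | 50/80 | 0.0507 |
| 0.70 | 0.0500 | 56/80 | 0.0502 |
| – | – | 58/80 | 0.0500 |
| 0.75 | 0.0497 | 60/80 | 0.0499 |

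**5. Paired t-test at 40 then 80 pairs, simulated under the null (600 million runs, error about 0.00001).**

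| Rule | α |
|---|---|
| p < .0054, then p < .0492 | 0.0515 |
| p < .0052, then p < .0480 | 0.0503 |
| t statistic against 2.782, then 1.967 | 0.0565 |
| t statistic against 2.797, then 1.977 | 0.0552 |

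The constants account for 0.0513 − 0.0500 = 0.0013 on the normal scale, and 0.0515 − 0.0503 = 0.0012 from the rounded t-test figures (about 0.13 points before rounding). The larger figures in the last two rows are mostly scale mismatch: t = 1.967 on 79 degrees of freedom has p = .0527, not .0492.

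**6. Effect on decisions.** With p-value cut-offs and SD 5.7, the mean change needed is t × 5.7/√n:

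- Interim, n = 40: 2.946 × 0.901 = 2.66 with .0054; 2.961 × 0.901 = 2.67 with .0052.
- Final, n = 80: 1.998 × 0.637 = 1.273 with .0492; 2.009 × 0.637 = 1.280 with .0480.

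The two p-value rules disagree in 0.13% of trials under the null and 0.31% under the planned effect.

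**The case against.** The strongest reply is that the excess is trivial. A level stated to the whole percent covers 5.13%. The study is single-arm, and section 1.2.2 says its results will feed the planning of a later randomized study. The smallness is real, and it limits the weight of the point. It does not make the thresholds right: they are pre-specified to four decimals, and they miss the level they are meant to hold.

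Second, the trigger counts participants who have had CALM, not those with 6-month scores, so the information fraction is not fixed, and by about 70% the excess is gone. That qualifies the figure. Half-way is still the natural reading, and an earlier look makes matters worse (0.0519 at 40%).

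Third, 0.0565 requires comparing a raw t statistic with the printed values, when the nominal levels beside them could equally be applied to the t-test p-value. Agreed. That is a separate clarification and no evidence against the constants, since the correct pair read the same way gives 0.0552.

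Fourth, the second count of interims looks like a slip for two analyses in total. Also agreed: the single trigger, the two cut-offs, their √2 ratio and section 8.3.2 all fit one interim plus one final. Nothing in the documents says so, however, and the sentence needs correcting.

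**Conclusion.** The point holds. With the look at half information, 2.782 and 1.967 give an overall two-sided alpha of 0.0513 (normal scale) or 0.0515 (as t-test p-value cut-offs), not the 5% stated in the same paragraph. The excess due to the constants is about 0.13 percentage points. It would alter a conclusion only for a result falling between the two sets of cut-offs. It rests on a half-way look measured in evaluable pairs, and disappears at about 70% information on the normal scale or 58 of 80 pairs with p-value cut-offs.

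The unspecified scale is a separate defect with a larger possible effect (0.0565). The contradictory count of interims is an error of wording. None of this is serious alone, but the paragraph governs early stopping and the primary claim, and should be corrected.

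**What to change.** Amend 8.3.1 to say the following:

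- There is one interim and one final analysis, two in total. Delete the reference to two interims.
- The interim takes place when 40 of the planned 80 evaluable participants have both baseline and 6-month PROMIS-Depression scores. This is what makes the information fraction one half.
- Both analyses use the two-sided paired t-test p-value. Stop for benefit if p < .0052 at the interim; claim success at the end if p < .0480.
- If the counts differ from 40 or 80, the interim level stays at .0052 and the final level is re-solved for an overall two-sided 0.05 at the actual fraction (interim pairs divided by final pairs). This gives .0476 at 35/80, .0484 at 45/80 and .0488 at 50/80.

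Two limits should be understood. Away from 40/80, a fixed interim level is no longer strictly O'Brien-Fleming, although alpha is still controlled. And because the levels are derived on the normal scale, the t-test alpha is 0.0502 to 0.0503. If a spending function is preferred, use it for every count and name it in full, including whether alpha is spent per tail, since the two versions in the table above differ.

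Cost: a few numbers and sentences, and no extra participants. With p-value cut-offs, power at n = 80 goes from 79.7% to 79.4%, and the chance of stopping at the interim under the planned effect from 18.9% to 18.5%. Power is then best stated as about 79%. Most of the gap to 80% comes from the t-test itself, which gives 79.7% at 80 pairs with no interim.

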1.2 BACKGROUND AND RATIONALE

1.2.1 Psychological distress

Psychological distress is estimated to affect between 30% and 73% of patients with primary malignant brain tumors (1, 2) (3). Limited data exists in the primary spine tumor patient population, but a recent unpublished analysis of data collected as part of the NOB-Natural History Study on 73 patients revealed that 38% reported moderate-severe distress on the M.D. Anderson Symptom Inventory-Spine Tumor (MDASI-SP), and 23% moderate-severe anxiety and 14% moderate-severe depression using PROMIS self-report instruments. Distress is usually under-identified in brain tumor patients (4) (5) and has been found to persist across the illness trajectory (6). Mood disturbance in glioma patients has been found to be similar to breast cancer populations (7). Several

research findings have reported the associations between emotional distress with performance status and psychotropic medication use (8) (9), emotional distress in survivorship (8), symptom burden in minority CNS patients (10), sleep disturbance effects on mood interference (11), increased mood disturbance association with low hope (12), confirming the distress glioma patients experience. The majority of studies in PCNST patients has been cross-sectional or retrospective in nature (13-15), but indicate that depressive symptoms commonly occur in approximately a third of patients. The few longitudinal studies that have been done, indicate that patients remain with symptoms through the follow-up period (3 and 6-month time point)(14, 15).

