Understanding the effects of CALM using telepsychology in this patient population will help in identifying feasible methods in treating patients' distress and will be used to calculate sample size and effect for a multicenter randomized study, evaluating CALM versus standard of care in the PCNST patient population. This can allow for more tailored psychosocial interventions focused on patients' needs and can provide additional coping mechanisms utilized throughout the illness trajectory in dealing with challenges associated with a PCNST diagnosis.

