2 ELIGIBILITY ASSESSMENT AND ENROLLMENT

2.1 ELIGIBILITY CRITERIA

2.1.1 Inclusion Criteria

- Subjects with histological or imaging confirmation of PCNST who are undergoing standard of care or experimental treatment.
- Adults (≥ 18 years of age) who are English-speaking
- Subjects who have a life expectancy of at least 3 months from time of study entry to allow for participation in the 3 required sessions.
- Subjects must be enrolled on the Neuro-Oncology Branch Natural History Study 16C0151.
- The ability of the subject to understand and the willingness to sign a written informed consent document as determined by the assessment of the treating physicians.

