2.3.1 Treatment Assignment Procedures

Cohorts

Number	Name	Description
1	Cohort 1	Participants diagnosed with a primary central nervous system tumor who are undergoing standard of care or experimental treatment.

Arms

Number	Name	Description
1	CALM intervention (remote)	All sessions and patient outcome questionnaires will be completed remotely.

Participants in Cohort 1 will be directly assigned to Arm 1.

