3 STUDY IMPLEMENTATION

3.1 STUDY DESIGN

This protocol is a single-arm design and will implement CALM therapy in PCNST patients currently enrolled in the NIH trial 16C0151. Study enrollment, treatment, and all study procedures will be done remotely. Only ISSO approved telehealth platforms will be utilized for telehealth procedures.

All telehealth/remote procedures used in this protocol will be consistent with applicable NIH policies (e.g., Medical Administrative Series policy, M20-1 found at: <https://cc-internal2.cc.nih.gov/policies/PDF/M20-1.pdf>).

Because our outcome measures (depression, distress, quality of life) are affected by recurrence, we will try to enroll an adequate representation of participants with recurrence and no recurrence.

Participants will be assigned to a CALM therapist and complete baseline questionnaires before starting CALM therapy. Prior to the completion of each session, future sessions will be scheduled with the participant.

CALM includes 3-6 individual therapy sessions, each approximately 45-60 minutes in length, delivered over 6 months. Additional sessions may be offered if clinically indicated while the participant is on the study, with the CALM domains being revisited if the participant is still experiencing challenges and the CALM therapist identifies this need to help the participant process any additional feelings. A maximum of 3 booster sessions will be offered. These additional sessions may be offered if clinically indicated while the participant is on the study.

Prior to each session, CALM therapist will confirm that participant is at home address on file and will have the contact information for a patient identified contact (either living in the home or primary contact outside of the home) and local provider. If the participant is showing signs of being in danger to themselves or others, the participant's location will be confirmed, the patients contact (living in the home or outside) will be contacted by phone and a brief safety plan (identify coping strategies, provide professional emergency contacts) will be created to minimize risk of harm. The CALM therapist will stay in contact with the participant until identified contact or healthcare provider has been reached and they can continue on with management of the participant's care. The information collected from the participant (location, if identified contact is in the home or not) will be provided to the health care provider identified by the participant.

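### Section 8.3.1 turns a single-arm test of change from baseline into a claim that CALM works; the 5% error rate covers no change from baseline, not no effect of CALM

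*Combined protocol and SAP*

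**What the plan says.** Section 3.1 states: "This protocol is a single-arm design". Section 2.3.1 agrees: "Participants in Cohort 1 will be directly assigned to Arm 1". For the primary endpoint, Section 8.3.1 says "we will perform a paired t-test from baseline to 6 months using a 2-tailed test at a 5% significance level". It names no reference change, historical benchmark or minimum difference, so the null value is zero change.

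The same section fixes what a significant result means. One interim analysis takes place when half the participants have been treated. If the absolute statistic exceeds 2.782, the study stops and CALM is said to be beneficial. If the absolute statistic exceeds 1.967 at the final analysis, "At the end of the study, CALM treatment will be claimed to be a success". Sections 1.1.1 and 8.1 word the primary objective as demonstrating the effects of CALM. Sections 8.3.2 and 8.3.3 label differences from baseline as the immediate and long-term CALM effect. No section limits this causal reading.

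The last paragraph of Section 1.2.2 says that what is learned here "will be used to calculate sample size and effect for a multicenter randomized study" comparing CALM with standard of care.

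**The concern.** A paired test against zero answers whether the average score moved. It does not say why. The protocol names several influences other than CALM. Section 3.1 says recurrence affects depression, distress and quality of life. Section 4 places no restriction on medication. Section 2.1.1 requires participants to be undergoing standard or experimental treatment, and Section 6.1 shows that newly diagnosed, recurrent and surveillance patients are mixed. Without a comparator, any net movement from these sources is added to whatever CALM does.

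At stake is the meaning of the headline result. If scores fall for other reasons, the rule in Section 8.3.1 credits CALM. If they rise because disease progresses, a real benefit can be hidden and the rule counts against CALM. Either way the verdict has no known error rate for the question it claims to answer.

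**Working it through.** **Inputs.** From Section 8.2: expected mean reduction 1.8, SD of the difference 5.7, two-sided 5%, 80% power, 80 evaluable, 20% attrition. From Section 8.3.1: boundaries 2.782 (interim) and 1.967 (final), both on the absolute statistic. Assumed: the interim falls at half the information (40 of 80 pairs), and the size of any change not due to CALM. The documents give no figure for the latter.

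**Step 1: reproduce the plan's sample size.** The one-sample formula is n = (SD × (z0.975 + z0.80) / change)² = (5.7 × (1.960 + 0.842) / 1.8)² = 78.7, rounded up to 79. With the exact noncentral t, power at n=80 is 79.7%, and 81 are needed to reach 80%. The stated 80 is reproduced within rounding, and 80 / (1 − 0.20) = 100 recruited. This confirms that the study is sized for change against zero.

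**Step 2: what observed change earns the verdict.** The standard error at n=80 is 5.7 / √80 = 0.637. The final rule is met by a mean change of 1.967 × 0.637 = 1.25 points. At the interim, 2.782 × 5.7 / √40 = 2.51 points are needed.

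**Step 3: chance of crossing either boundary when CALM has no effect.** Let b be an assumed mean fall from other causes. The final statistic has mean b / 0.637, the interim statistic has that mean × √0.5, and their correlation is √0.5 (normal approximation).

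| Assumed fall b (points) | Mean of final statistic | Mean of interim statistic | Chance of crossing |
|---|---|---|---|
| 0 | 0 | 0 | 5.1% |
| 0.45 | 0.706 | 0.499 | 11% |
| 0.9 | 1.412 | 0.999 | 29% |
| 1.25 | 1.961 | 1.387 | 50% |

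Ignoring the interim and using a single two-sided paired t-test at 5%, the last three rows become 11%, 29% and 49%, so the result does not depend on the interim look.

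**Step 4: the opposite direction.** The same calculation covers masking. If CALM truly lowers scores by 1.8 but disease course raises them by an assumed 0.9, the net fall is 0.9 and the chance of crossing is 29%. Without the rise it would be 81%.

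**Step 5: precision of the change itself.** The 95% confidence interval half-width at n=80 is 1.990 × 0.637 = 1.27 points.

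**The case against.** The sponsor can fairly say that the study is framed as early work. The précis speaks of preliminary effectiveness, Section 8.3.2 of preliminary data for later studies, and Section 1.2.2 plans a randomized comparison next. A single-arm pilot is legitimate, and success could be read as a go/no-go label. That context stands, but none of it changes the rule in Section 8.3.1, which is what would be followed and reported.

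The sponsor can also say that nothing in the documents shows scores falling on their own. Section 1.2.1 reports that symptoms persist at 3 and 6 months, and Section 2.1.1 sets no depression threshold, so regression to the mean from selecting high scorers is not built in. Both points stand. However, Section 1.2.1 gives no mean change or SD, so it does not establish that the change would be zero without CALM. Loss of sicker participants biases a paired comparison only if their change would have differed; that is a missing-data question.

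A reader might infer from Section 1.2.2 that the pre-post mean will be used as the between-arm difference. On that reading, a trial planned on 1.8 (about 158 per arm, assuming SD 5.7 in each) would have 29% power if the net difference were 0.9. The text says that sample size and effect will be calculated but does not say how, and Section 1.2.2 also describes an earlier randomized trial of CALM against usual care. The power figure needs both an inferred plan and an assumed halving, so only a request for clarification is justified.

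A reader might also infer that a natural-history comparison is ready to hand, because Section 2.1.1 states "Subjects must be enrolled on the Neuro-Oncology Branch Natural History Study 16C0151". The evidence of PROMIS data there, "14% moderate-severe depression using PROMIS self-report instruments", is a percentage from 73 patients with spine tumors. It shows no serial scores, and note 2 of the Section 3.4 calendar allows reuse of questionnaires from that study only for the MDASI and EQ-5D.

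**Conclusion.** The point holds as a mismatch between the conclusion in Section 8.3.1 and the design. It is not an arithmetic error: the sample size reproduces, and the chance of crossing with truly zero change is close to the nominal 5%. That protection does not extend to the statement that CALM caused the change. How far it falls short depends on change not due to CALM, whose size and direction the documents do not give. The 11%, 29% and 50% are therefore illustrations under assumed falls of 0.45, 0.9 and 1.25 points, with SD 5.7, 80 pairs and equally spaced looks.

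Two stronger readings should be resisted. One is that the plan is biased in favour of CALM; recurrence and progression could equally bias against it. The other is that the trial needs a control arm; its aims of describing change and informing a randomized trial can be met with one arm once the conclusion is restated. The change is worth making because it alters what the trial may conclude at almost no cost.

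**What to change.** In Section 8.3.1, replace the benefit claim at the interim and the success claim at the end with a statement that a mean reduction from baseline was observed, reported with its 95% confidence interval, and not attributed to CALM in the absence of a control.

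In the last paragraph of Section 1.2.2, state that this study supplies the SD of change, attrition and session uptake for the randomized trial, and that the between-arm difference will come from controlled evidence or a minimum important difference.

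Optionally, add a supportive comparison with 16C0151 participants who do not receive CALM, only if serial PROMIS-Depression scores exist for them. Recruitment is by invitation (Section 2.1.3), so that group would include people who declined, and the comparison would carry its own selection bias.

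The required changes are wording only; no trial procedure or sample size changes. The cost is a less favourable headline claim, plus one secondary analysis if the optional comparison is feasible.
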